6.10.4 Subgroup Analyses

Page 29 of 61 Confidential

Assessment of exposure across gender, ethnicity and age will be explored using the steady state PK parameters AUC_{0-168,ss} and C_{max,ss}. Subset analyses will include treatments B and C only.

Gender Analysis

To assess exposure across gender, adding gender and gender by treatment interaction to the bioequivalence models allows for testing gender effects across and within the study treatment. In the model, gender and gender by treatment interaction effects will be estimated using least squares means and tested using a significant level of alpha = 0.05. The following SAS code details the testing approach within the standard BE models:

In addition, box-plots of the parameters will be generated for each treatment by gender.

Ethnicity Analysis

Similar to gender above, effects of ethnicity (Hispanic or Latino vs. Not-Hispanic or Latino) will be explored.

Age Analysis

To examine the potential effect of age on donepezil steady-state PK for the B and C treatments, a three-step assessment procedure will be undertaken:

1. Test slopes-equal-to-zero hypothesis for each treatment: This is designed to determine if a model without the covariate of age can be used to adequately describe the PK parameters (i.e. test the slopes-equal-to-zero hypothesis for each treatment). To achieve this objective an additional fixed effect (age*treatment) will be added to the Treatment B vs. Treatment C ANOVA model described in Section 6.10.1. If the hypothesis that all

Page 30 of 61 Confidential

slopes are zero is accepted, a common slope model will be fit to the data and the slopeequal-to-zero hypothesis will be tested (Step 3 below).

- 2. If the hypothesis that all slopes are equal to zero was rejected in Step 1 (i.e. 1 or more of the slopes were not 0), the hypothesis that the slopes are equal will be tested. An ANCOVA will be performed on the natural logarithms of the PK parameters with age being added to the model used in Step 1. If the slopes are determined to be unequal, the treatment-specific slopes and intercepts from the unequal slopes model (Step 1) will be used to describe the relationship between age and the natural log transformed PK parameter for each treatment.

For effects of gender or ethnicity on exposure the least squares geometric means (LSGM) of the PK parameters for each gender or each ethnicity group will be reported. Point estimates and 90% Confidence Intervals (CI) for the ratios of geometric means (Female vs. Male or Hispanic or Latino vs. Not-Hispanic or Latino) will be provided. The results from Type 3 Tests of Fixed Effects will also be reported with p-values to indicate if significant effects from gender, ethnicity, or age for each treatment exist.

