6.10.1 Statistical PK Comparison between Treatments

Statistical comparison of the PK parameters of donepezil and 6-O-desmethyl donepezil exposure ($AUC_{0.24,ss}$, $AUC_{0-168,ss}$, $C_{max,ss}$, $C_{min,ss}$, $C_{tau,ss}$, $C_{avg,ss}$, and FLUCP,ss) at steady-state will be performed using an Analysis of Variance (ANOVA) model for a 2-way crossover design for the comparison of 10 mg TDS vs. Aricept (Treatment B vs. Treatment C) on the ln-transformed data with sequence, period and treatment as the fixed effects and subject within sequence as a random effect. For comparison of 5 mg/day TDS vs. Aricept (Treatment A vs. Treatment C) the analysis will be performed using a ANOVA model with treatment as fixed effect and subject as random effect with Treatment A being dose normalized (PK parameter values multiplied by 2) before the analysis. A statistically significant difference is defined as p <0.05.

Geometric means. inter-subject and intra-subject variability (coefficient of variation in percent, CV_{intra} % and CV_{inter} %, respectively), and intraclass correlation (Chow and Liu, 2009)⁴ of the PK parameters will be calculated based on the mixed model results (Proc Mixed of SAS) as indicated below:

Page 90

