Corium, Inc. CL-P-20003 Statistical Analysis Plan Version 2.0 Issue Date 15-JUL-2021

Table Number	Table Title	Validation	Shell Number
		Method	(if repeat)
14.4.27	Attainment of Steady State for Trough		
	Donepezil (Combined Periods) - PK Population		
14.4.28	Subgroup Analysis: Comparison of Males and	IP	
	Females within Treatment for Donepezil		
	Pharmacokinetic Parameters at Steady State -		
	Relative Bioavailability Population		
14.4.29	Subgroup Analysis: Comparison of Ethnic	IP	
	Subgroups within Treatment for Donepezil		
	Pharmacokinetic Parameters at Steady State -		
	Relative Bioavailability Population		
14.4.30	Subgroup Analysis: Relationship of Age to	IP	
	Natural Log Transformed Donepezil		
	Pharmacokinetic Parameters at Steady State -		
	Relative Bioavailability Population		
14.5	PD Tables		
14.6	Other Data		

Corium, Inc. CL-P-20003 Statistical Analysis Plan Version 2.0 Issue Date 15-JUL-2021

Figure Number	Figure Title	Validation Method	Shell Number (if
			repeat)
14.4.1	Mean Plasma Donepezil Concentration-Time Data in	IP	
	Plasma (Week 5) after 5 mg/day and 10 mg/day TDS		
	Application on Week 5 (Days 29-36 Following TDS		
	Application) and after QD Administration of 10 mg		
	Aricept for Week 5 (Days 35-36 Following First		
	Dose) on Linear Scale - PK Population		
14.4.2	Mean Plasma 6-O-Desmethyl Donepezil	IP	
	Concentration-Time Data in Plasma (Week 5) after 5		
	mg/day and 10 mg/day TDS Application on Week 5		
	(Days 29-36 Following TDS Application) and after		
	QD Administration of 10 mg Aricept for Week 5		
	(Days 35-36 Following First Dose) on Linear Scale -		
1440	PK Population		
14.4.3	Mean Plasma 6-O-Desmethyl Donepezil to Donepezil	IP	
	Concentration Ratios after 5 mg/day IDS Application		
	on Week 5 (Days 29-36 Following TDS Application)		
1444	On Linear Scale - PK Population	ID	
14.4.4	Concentration Detion often 10 mg/day TDS	IP	
	Application on Weak 5 (Days 20.26 Fallowing TDS		
	Application on Views 5 (Days 29-50 Following TDS		
1445	Mean Plasma 6 O Desmethyl Donenezil to Donenezil	ID	
14.4.3	Concentration Ratios after OD Administration of 10	11	
	mg Aricent for Week 5 (Days 35-36 Following First		
	Dose) on Linear Scale - PK Population		
1446	Mean Steady-State Plasma Donenezil Concentration-	IP	
11.1.0	Time Data in Plasma (Week 5) after 5 mg/day and 10	п	
	mg/day TDS Application on Week 5 (Days 29-36		
	Following TDS Application) and after OD		
	Administration of 10 mg Aricept for Week 5 (Days		

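### SAP 6.10.4 reads Type 3 p-values as gender or ethnicity effects within each treatment, but neither Type 3 test in that model answers that question

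*SAP*

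**What the plan says.** SAP 6.10.4 explores AUC0-168,ss and Cmax,ss across gender, ethnicity and age, and limits the data to the 10 mg TDS (B) and Aricept (C): "Subset analyses will include treatments B and C only". The base model is the B-versus-C crossover analysis of SAP 6.10.1, fitted "on the ln-transformed data with sequence, period and treatment as the fixed effects and subject within sequence as a random effect".

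For gender, the SAP says that "adding gender and gender by treatment interaction to the bioequivalence models allows for testing gender effects across and within the study treatment", and that "gender and gender by treatment interaction effects will be estimated using least squares means and tested using a significant level of alpha = 0.05". Ethnicity takes the same form: "Similar to gender above, effects of ethnicity (Hispanic or Latino vs. Not-Hispanic or Latino) will be explored". Age has its own three-step slope procedure.

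The section closes by promising geometric least squares means for each gender or ethnicity group, and female/male and Hispanic/not-Hispanic ratios with 90% CIs. It does not say that these ratios are given by treatment. The last sentence adds Type 3 results: "The results from Type 3 Tests of Fixed Effects will also be reported with p-values to indicate if significant effects from gender, ethnicity, or age". Read through to its end, the operative part is "p-values to indicate if significant effects from gender, ethnicity, or age for each treatment exist".

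In the SAP 9 table list, the title of Table 14.4.28 begins "Subgroup Analysis: Comparison of Males and" and continues as a within-treatment comparison of the sexes. Table 14.4.29 is titled the same way for ethnic subgroups.

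**The concern.** The question posed is whether women and men (or the two ethnic groups) differ in exposure on the TDS, and separately whether they differ on Aricept. The p-values named for answering it come from tests with other null hypotheses. A report that follows the closing sentence literally would attach a p-value to a statement about one product that the p-value does not test.

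Three things can then go wrong:
- An effect present only on the TDS is halved in the main-effect test. If that test is significant, it can be read as an effect on Aricept as well.
- Equal effects on both products leave the interaction null true, so the interaction p-value says nothing about whether either product shows an effect.
- Opposite effects on the two products cancel in the main-effect test.

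**Working it through.** **What each test addresses.** Let dB and dC be the female-minus-male differences in mean log exposure on the TDS and on Aricept. With gender and gender-by-treatment both in the model:
- Type 3 gender: null (dB + dC)/2 = 0.
- Type 3 interaction: null dB − dC = 0.
- The per-treatment statements need dB = 0 and dC = 0, tested separately.

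This follows from the model as described and needs no variance assumption. Ethnicity is identical in form.

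**Inputs.** From SAP 4: 48 completers and a CV of 29% for AUC. From SAP 6.10.4: alpha 0.05. Assumed, because the documents give no value: a 24/24 gender split, between-subject CV of 20% to 50%, and a female/male ratio of 1.25 on the TDS with 1.00 on Aricept.

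**The plan's own figure.** Treat 29% as the within-subject CV: sw² = ln(1 + 0.29²) = 0.0808, so sw = 0.284. Two one-sided tests in a 2×2 crossover, true ratio 1.05, limits 0.80 to 1.25, give power of 90.4% at 48 subjects (89.3% at 46). The stated power of at least 90% reproduces, which supports reading the 29% as within-subject. The SAP states no power for the subgroup tests.

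**Power formulas.** d = ln(1.25) = 0.2231 and sb² = ln(1 + CVb²). With 24 per gender, SE² = V × (1/24 + 1/24) = V/12, with about 45 df.
- Main effect: size d/2 = 0.1116, V = sb² + sw²/2.
- Interaction: size d, V = 2sw².
- Within-TDS contrast: size d, V = sb² + sw².

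Worked case, CVb = 20% (sb² = 0.0392):
- Main effect: V = 0.0796, SE = 0.0814, noncentrality 0.1116/0.0814 = 1.37, rejection 27%.
- Interaction: V = 0.1615, SE = 0.1160, noncentrality 1.92, rejection 47%.
- Within-TDS: V = 0.1200, SE = 0.1000, noncentrality 2.23, rejection 59%.

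| Between-subject CV | 20% | 30% | 40% | 50% |
|---|---|---|---|---|
| Type 3 gender significant | 27% | 19% | 14% | 11% |
| Type 3 interaction significant | 47% | 47% | 47% | 47% |
| Gender significant, interaction not | 14% | 10% | 7% | 6% |
| Within-TDS contrast significant | 59% | 46% | 35% | 28% |
| Within-Aricept contrast significant | 5% | 5% | 5% | 5% |

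The third row comes from 40,000 simulated trials per case. In balanced data the main-effect and interaction tests are nearly independent, so a product check applies: 0.268 × (1 − 0.469) = 0.142, against 0.139 simulated. The simulation also reproduced the other rows.

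**Other cases.**
- TDS-only ratio 1.5: main effect 68% to 27%, interaction 93%, main effect without interaction 5% to 2%, within-TDS contrast 98% to 70%.
- TDS-only ratio 1.25 with a 12/36 split: main effect 21% to 10%, interaction 37%, within-TDS contrast 47% to 22%.
- Ratio 1.25 on both products, between-subject CV 30%: main effect 57%, interaction 5%, each within-treatment contrast 46%.
- Ratio 1.25 on TDS and 0.80 on Aricept: main effect 5%, interaction 96%.

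**The case against.** The strongest reply is that within-treatment comparisons already appear to be intended. Both effects are to be estimated with least squares means, box plots are planned for each treatment by gender, Tables 14.4.28 and 14.4.29 are titled as within-treatment comparisons, and the Type 3 results are additional to ratios and CIs. The SAS code that would show whether within-treatment contrasts are requested is missing from the public copy, which is not a fault in the plan. A reader might infer that the SAP provides no within-treatment comparison at all; the documents do not support that. What remains is that the closing sentence assigns the wrong meaning to the Type 3 p-values whatever the code contains, and the text names no other p-value for the per-treatment question.

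A reader might also infer that a TDS-only effect will be charged to Aricept and usually missed for the TDS. That goes too far. It supposes that the main-effect p-value is read alone, whereas the plan also tests the interaction at 0.05. Reading both lowers misattribution to 14% to 6% at ratio 1.25 and 5% to 2% at ratio 1.5, and opposite effects are flagged in 96% of trials. Nor is the within-TDS contrast a sensitive instrument: at ratio 1.25 it misses the effect in 41% to 72% of trials. From a between-subject CV of 30% upward, the interaction test detects a TDS-only effect about as often or more often, although it cannot say which product is responsible.

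Extending the point to age is not supported either. Age has a separate procedure whose first step tests the treatment-specific slopes jointly, and those slopes are used when found unequal.

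**Conclusion.** The point holds for gender and ethnicity as an error of interpretation in SAP 6.10.4: the Type 3 tests address the average effect and the difference in effect between products, not an effect within either one. That part rests on the model description alone.

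The size rests on the assumptions in the working. With a TDS-only ratio of 1.25, a statement about Aricept would be wrong in 27% to 11% of trials if the main effect is read alone, and in 14% to 6% if it is read only when the interaction is not significant, against a nominal 5%. The figures use the AUC variability in SAP 4. Nothing comparable is given for Cmax,ss, and no ethnicity split is stated, so the size for ethnicity is not established. The subgroup work is exploratory, and neither the primary bioequivalence conclusion nor its power depends on it.

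**What to change.** In SAP 6.10.4, replace the Type 3 sentence for gender and ethnicity with wording to this effect: the subgroup effect within each treatment will be estimated and tested by the within-treatment contrast of the subgroup-by-treatment least squares means from the same model (Female/Male and Hispanic/Not-Hispanic, within B and within C), reporting the ratio, 90% CI and p-value; the Type 3 tests will be described only as the effect averaged over B and C and as the subgroup-by-treatment interaction.

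Base Tables 14.4.28 and 14.4.29 on these contrasts, which brings the text into line with their titles. Leave the age procedure unchanged.

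The cost is a sentence in the SAP and, if not already in the code, a contrast statement in the existing model; no new data are needed. The downside is two contrasts per factor for each PK parameter in place of one main-effect p-value.

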6.11 Safety Analyses

The safety analyses will be presented by the treatment received for the Safety Population.

6.11.1 Adverse Events

A treatment emergent adverse event (TEAE) is defined as:

- Any AE that has a new onset during the study between the initiation of study drug and the follow-up visit.
- Any pre-existing AE that has worsened in severity on or after the initiation of study drug till the follow-up visit.

The following rules will be used to assign a TEAE to a treatment:

- A TEAE will be assigned to the treatment received immediately before onset.
- Any TEAE reported within Period 1, Day 36, when no treatment is administered, will be attributed to the last treatment received before Day 36 began.
- If the severity of a TEAE increases in a later period the TEAE at the increased severity also will be assigned to the treatment received immediately before the increase in severity.

Page 33 of 61 Confidential

All TEAEs are defined as being definitely, probably, possibly related or unrelated to the study drug. If an AE has missing relationship it is assumed to be definitely related to the study drug for analysis purposes. Additionally, any SAE considered definitely, probably, or possibly related to the study drug will also be classified by the Sponsor as either "expected" or "unexpected" upon review by the medical monitor.

Adverse event severity will be graded as Grade 1: Mild, Grade 2: Moderate, or Grade 3: Severe or Medically Significant but not immediately life-threatening. Maximum severity will be assumed for an AE with missing severity.

All AEs will be coded using the most current version of the Medical Dictionary for Regulatory Activities (MedDRA version 23.1, updated to include activities related to COVID-19) by SOC and PT.

The following tables will be presented for AEs by treatment and overall using the Safety Population:

- Overall incidence and the number of AEs, SAEs, TEAEs leading to withdrawal.
- TEAE by system organ class and preferred term, incidence and number of events
- Treatment related TEAE by system organ class and preferred term, incidence and number of events
- Serious TEAE by system organ class and preferred term, incidence and number of events and "expected or unexpected" classification
- TEAE by system organ class and preferred term by nearest relationship to study drug, incidence and number of events
- TEAE by system organ class, preferred term and maximum severity, incidence
- TEAEs leading to early withdrawal by system organ class and preferred term, incidence
- Listing of Serious TEAEs (presented in the Table section of the appendices)
- Listing of Deaths (produced only if necessary and presented in the Table section of the appendices)
- Listing of TEAEs leading to early termination by system organ class and preferred term, incidence

In counting the number of AEs reported, a continuous event (i.e. reported more than once and which did not cease), will be counted only once; non-continuous AE reported several times by the same subject will be counted as multiple events.

Page 34 of 61 Confidential

If more than one AE is coded to the same preferred term for the same subject, the subject will be counted only once for that preferred term using the most severe and most related occurrence for the summarization by severity and by relationship to the study drug.

All AEs will be listed.

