1 INTRODUCTION

This document details the planned statistical analyses for the *Corium, Inc.*, protocol "*CL-P-20003*" study titled "A Phase 1, Open-Label, 3-Period, Randomized, Crossover Pharmacokinetic Study to Evaluate the Steady-State Pharmacokinetics of 5 mg and 10 mg Corplex™ Donepezil Transdermal Delivery Systems Compared to 10 mg Oral Administration of Aricept® in Healthy Volunteers".

The proposed analyses are based on the contents of the final version of the protocol (dated *2-OCT-2020*), the protocol amendment #1 (*dated 26-OCT-2020*), and the protocol clarification memo #1 (*dated 30-OCT-2020*).

This is a Phase 1, open-label, randomized, 3-period, 3-treatment, crossover pharmacokinetic study to evaluate the steady-state pharmacokinetics of 5 mg/day and 10 mg/day CorplexTM Donepezil TDS manufactured with the commercial process compared to 10 mg oral administration of Aricept[®] in healthy volunteers.

The study will consist of a Screening Period, a Treatment Phase with 3 treatment periods and a Follow-Up visit as follows:

- Screening Period: Subjects will undergo a Screening Period up to 28 days prior to entering the Treatment Phase.
- **Treatment Phase:** Eligible subjects will participate in 3 treatment periods each consisting of 36 days, without a washout between treatments:
 - Treatment A: 5 mg/day Donepezil Transdermal Delivery System (TDS) for 5 consecutive weeks (7-day wear for each of the 5 patches). In Period 1, all enrolled subjects will receive Treatment A. The last (5th) patch will be removed on the morning of Day 36 (168 hours after the last patch application). No study drug will be administered on Day 36. The 5 mg/day Donepezil TDS as the first treatment of the study allows subjects to get accustomed to the potential cholinergic effects (5 mg/day for 1 week is the recommended starting dose before titrating up, to 10 mg/day). In this study, the 5 mg/day Donepezil TDS is administered for 5 weeks to reach steady state in order to measure the steady state pharmacokinetics in Week 5 to be compared with those after oral Aricept[®].

Page 4 of 61 Confidential

During Treatment Periods 2 and 3, the subjects will be randomized to receive either sequences of Treatments B-C or Treatments C-B. Subjects will receive the following treatments according to the randomization schedule.

- **Treatment B:** 10 mg/day Donepezil TDS applied weekly (within ±1 hour of application time on Day 1) for 5 consecutive weeks.

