- **Treatment C:** 10 mg Aricept[®] donepezil tablet administered QD for 5 weeks (within ±1 hour of dosing time on Day 1).

Randomization to the 2 treatment sequences will be stratified by the subject's gender. For all oral doses and TDS applications, subjects will receive a light meal 30 minutes prior to dosing. Standard meals will be provided at appropriate times thereafter. Blood samples for pharmacokinetics and safety assessments will be collected during the Treatment Phase.

In each period wherein the treatment consists of a patch, the subjects will wear a total of 5 patches for a total of 35 days (5 weeks). The last (5th) patch in the period will be removed after the morning blood draw on Day 36 (168-hour time point after the last patch in the period). No treatment will be administered on Day 36 of the period; additional post-wear PK blood samples will be collected on Day 36 after any patch treatment. Because of the potential for continued drug absorption after TDS removal, an additional non-treated PK sampling day (Day 36 in each treatment period) was added to the PK sampling schedule after TDS removal at the end of the TDS dosing interval (168 hours) to evaluate the presence of this phenomenon. These samples at the very beginning of the terminal phase will not be used for any terminal-phase assessments due to their truncated nature.

In each period (Period 2 or 3) wherein the treatment consists of oral Aricept[®], the subjects will an oral dose daily for a total of 35 days (5 weeks). The last oral dose in the period will be administered on the morning of Day 35. No treatment will be administered on Day 36 of the period; a PK blood sample will be collected in the morning of Day 36 at 24 hours after the last oral dose.

In Period 1, all subjects will wear patches (Treatment A). In Periods 2 and 3, subjects will either wear patches (Treatment B) or receive once-per-day oral Aricept[®] (Treatment C).

- The treatment in Period 2 will start on the morning of Study Day 37 after the predose blood draw for Period 2 is collected. No treatment will be administered on Study Day 72. For the patch treatment in Period 2, the patch will be removed on Study Day 72 after the 168-hour blood sample collection.
- \circ The treatment in Period 3 will start on the morning of Study Day 73 after the pre-

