dose blood draw for Period 3 is collected. No treatment will be administered on Study Day 108. For the patch treatment in Period 3, the patch will be removed on Study Day 108 after the 168-hour blood sample collection.

• Follow-Up: 5 ±2 days after the day of the last oral drug administration or last TDS removal during the Treatment Phase, subjects will enter a Follow-Up Visit to evaluate safety parameters.

There will be no washout phase between treatment periods (with the exception of Day 36 within each period to collect post-treatment PK blood samples).

Subjects will participate in the study for up to 144 days, including up to 28 days of screening, a Treatment Phase with 3 treatment periods of 36 days each, and a 5 \pm 2 day Follow-Up Visit. Eligible subjects will stay in the research clinic for 109 days (108 overnight stays) during the Treatment Phase.

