	Plasma 6-O-Desmethyl Donepezil to Donepezil Concentration Ratios after QD Administration of 10 mg Aricept for Week 5 (Days 35-36 Following First Dose) for Individual Subjects on Linear Scale - PK Population
Listing 16.2.1.1	Three columns were removed: "Safety Analysis Population", "Pharmacokinetic (PK) Population", and "Relative Bioavailability (BA) Population".
Listing 16.2.2.1	Added one column (PD Code) added Study Day to PD Date with a footnote: "# Study day relative to each treatment period start date"
Listing 16.2.3.1	Both PK Population and BA population were split into two columns (Primary and Secondary)
Listing 16.2.4.4	Added two columns: "Period Treatment" and "Assessment Date/Time (Study Day)"
Listing 16.2.4.6	Added two footnotes: 1) # Study day relative to each treatment period start date; 2) Note: Visits marked as "Extension Days" indicate a 7-8 day gap between the end of Period 2 (Day 36 relative to start of Period 2) and the start of Period 3
Listing 16.2.5.1	Listing title changed to: "TDS Application/Removal and Treatment C (Oral Aricept Tablets); One footnote added ":# Study day relative to each treatment period start date"; Treatment C was included in the listing.
Listing 16.2.5.2	Changed the Column header "Study Day" to "Visit" and added Study Day to "Sample Date/Time" column header [Sample Date/Time (Study Day)]
Listing 16.2.5.3	Added footnote: "# Study day relative to each treatment period start date"
Listing 16.2.6.10	Added Listing:
	Subjects Excluded from the Pharmacokinetic and Relative Bioavailability Populations
Listing 16.2.7.1	Added footnote: "# Study day relative to each treatment period start date"

QMD Ref: Worldwide-TMP-ST-008-2.0 Effective: 12Aug2019 Governing QMD: Worldwide-SOP-ST-001
Confidentiality Statement
This document is the property of Worldwide Clinical Trials Inc. and may not be duplicated copied, altered or removed from company without

This document is the property of Worldwide Clinical Trials Inc. and may not be duplicated, copied, altered or removed from company without prior approval from Worldwide Quality Assurance or in compliance with Worldwide Standard Operating Procedures.

100

Worldwide Clinical Trials Controlled Quality Management Document

WORLDWIDE	Sponsor:
CLINICAL TRIALS	Protocol Number:

Corium, Inc. CL-P-20003

POST DATABASE LOCK STATISTICAL ANALYSIS PLAN ADDENDUM

Listing 16.2.8.1	Added "Period Treatment" column and added a footnote: "# Study day
	relative to each treatment period start date"

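### By-treatment TEAE tables count 36 days for the 5 mg TDS but a mean of about 38 days for the 10 mg TDS and Aricept as planned, with no allowance for time at risk

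*SAP*

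**What the plan says.** SAP 6.11.1 defines a TEAE as "Any AE that has a new onset during the study between the initiation of study drug and the follow-up visit", and treats worsening of a pre-existing event in the same way. The attribution rule is "A TEAE will be assigned to the treatment received immediately before onset". It has no lag limit. The only rule for a drug-free day concerns Day 36 of Period 1, where an event "will be attributed to the last treatment received before Day 36 began".

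SAP 1 fixes the calendar. "In Period 1, all enrolled subjects will receive Treatment A", and "The treatment in Period 2 will start on the morning of Study Day 37". The 10 mg TDS (B) and Aricept (C) fill Periods 2 and 3 in either order. The Follow-Up Visit is 5 ±2 "days after the day of the last oral drug administration or last TDS removal during the Treatment Phase".

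The post-database-lock SAP addendum, in its change to Listing 16.2.4.6, adds a footnote that visits marked as Extension Days "indicate a 7-8 day gap between the end of Period 2" and the start of Period 3.

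The AE tables in SAP 6.11.1 give incidence and numbers of events by treatment and overall. The SAP's table list includes Extent of Exposure (Table 14.3.5.1), but no person-time denominator or exposure-adjusted rate is planned for the AE tables.

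**The concern.** The three treatment columns do not cover the same length of observation. The 5 mg column closes when the next treatment starts. The 10 mg TDS and Aricept columns also take the follow-up tail after Period 3 and any gap after Period 2. Under the attribution rule, those days can never be credited to the 5 mg TDS.

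The safety objective covers the once-weekly TDS, which is studied at both strengths. The tables put 5 mg, 10 mg and Aricept side by side, and a reader would naturally take an excess at 10 mg as dose-related. Part of such an excess could come from the longer window alone, and nothing planned would show how much.

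**Working it through.** **The plan's own calendar figure.** Protocol 6.2 gives up to 144 days: 28 (screening) + 3 × 36 + 7 (latest follow-up) = 143, or 144 with discharge Day 109. The calendar reproduces. The documents give no AE observation time per treatment, so it is derived here.

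**Inputs.** Period starts are Study Days 1, 37 and 73 (SAP 1). The last oral dose in Period 3 is Day 107 (Protocol, Treatment Phase Schematic) and the last TDS removal is Day 108 (SAP 1). Follow-up is 3, 5 or 7 days later. Assumptions: completers only, equal numbers in the two sequences, and the Follow-Up Visit day counted.

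**Window** = last attributable day − first dosing day + 1.

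- A (5 mg TDS): 36 − 1 + 1 = 36 days.
- Period 2, no gap: 72 − 37 + 1 = 36 days. With 7-8 extra days: 43-44.
- Period 3, B: (108 + 5) − 73 + 1 = 41 days (39-43 over the visit window).
- Period 3, C: (107 + 5) − 73 + 1 = 40 days (38-42).

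**Mean per treatment** = (Period 2 window + Period 3 window) / 2.

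| Case | B | C | B/A | C/A | B/C |
|---|---|---|---|---|---|
| As planned | (36+41)/2 = 38.5 | (36+40)/2 = 38.0 | 1.07 | 1.06 | 1.01 |
| 7-day gap for all | (43+41)/2 = 42.0 | (43+40)/2 = 41.5 | 1.17 | 1.15 | 1.01 |
| 8-day gap for all | (44+41)/2 = 42.5 | (44+40)/2 = 42.0 | 1.18 | 1.17 | 1.01 |

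Over the ±2-day visit window, the excess over A is 3-10% as planned and 12-21% with the gap for all. If 7-8 days already includes the normal one-day step between periods, the Period 2 window is 42-43 days. The nominal means are then 41.5-42.0 (B) and 41.0-41.5 (C), an excess of 14-17%.

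**Effect on incidence at constant hazard.** For incidence p over 36 days, h = −ln(1 − p)/36, and incidence over d days = 1 − exp(−h·d). With p = 0.30:

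- d = 38.0 gives 31.4% and d = 38.5 gives 31.7%.
- d = 41.5 to 42.5 gives 33.7% to 34.4%.

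Expected event counts rise in proportion to the window: 6-7% as planned, 15-18% with the gap for all.

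**Break-even.** The excess disappears if mean daily hazard over the longer window, relative to Period 1, is 36/38.0 = 0.95 or 36/38.5 = 0.94 as planned, or 36/41.5 = 0.87 to 36/42.5 = 0.85 with the gap. With equal hazard over the common 36 days, this is the case in which the extra days carry no events.

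**The case against.** A reader might infer that crude rates will be higher at 10 mg by construction. The documents do not support that. Only the window is longer by construction. The tail follows the last dose or removal, dosing during the gap is not described, and the 5 mg TDS is always the first exposure, in subjects with no donepezil for 60 days (Protocol 7.2.2). Hazard could be lower in the later window, and the break-even reduction is only about 5-15%.

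A reader might also take 38-42 days as each subject's window. It is a mean over sequences. Individual completers run from 36 days (Period 2, no gap) to 44 (Period 2 with an 8-day gap). The upper figures rest on one footnote to the COVID-19 listing, which does not say how many subjects had the gap.

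Nor did the addendum's revised TEAE definition create the imbalance. Protocol 17.6 already had a tail of 5 days after the last dose. That is the same nominal length, taking TDS removal as the end of dosing. The change only made the tail variable.

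The remaining objections also carry weight. SAP 6.11.1 plans no between-treatment AE test. Comparisons with the 5 mg TDS are already confounded with dose, period and order. Listing 16.2.7.1 will give study day relative to each period's start, so late onsets can be found by hand.

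There is also a good reason not to move tail events out of the B and C columns. The protocol gives a half-life of about 70 hours, so five days is 120/70 = 1.7 half-lives and about 30% of drug remains. Skin sites are planned for checks to 72 hours after removal. Tail events can be treatment-related.

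What is left is an avoidable imbalance in observation time that the Extent of Exposure table does not correct.

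**Conclusion.** The attribution windows are unequal, and the planned AE tables are crude. As planned, the 10 mg TDS and Aricept are observed 6-7% longer on average than the 5 mg TDS. With the gap for all subjects this would be 15-18%. At equal daily hazard, crude incidence and counts are pushed up for the 10 mg treatments relative to the 5 mg TDS. The push is modest, and it shrinks or vanishes if hazard is lower in the off-drug days.

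The figures rest on completers, equal sequences and nominal follow-up. Early terminators have no Follow-Up Visit (Protocol 9.5.2), and the effect of dropout on person-time cannot be computed from the documents. The randomised comparison, 10 mg TDS against Aricept, differs by half a day (about 1%) and is essentially unaffected. Equal windows would not make the 5 mg comparison unconfounded. They would remove one distortion that can be removed.

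**What to change.** Keep the by-treatment TEAE tables of SAP 6.11.1 as planned, and add two outputs:

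1. Person-days at risk for each treatment under the attribution rule, with events per person-time. This also picks up dropout and the actual gap and follow-up lengths.
2. A version of the main TEAE table limited to onset or worsening from the first dose of the period through period Day 36. Show onsets in the Extension Days, and between the end of Period 3 and the Follow-Up Visit, separately under the last treatment received, so that no event is lost.

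A footnote should give the mean window per treatment and the number of subjects with the gap.

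The cost is one programming flag and one extra table, from onset and dosing dates already collected. SAP 6 allows additional tables with documented justification. Because the database is locked, label these as supplementary and added after lock. One limit remains: with no washout, late effects of the 5 mg TDS that start on or after Day 37 are still assigned to the next treatment, and neither output changes that.
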